measures planned for the full RCT (See upload of Baseline Clinician Measures); these measures will be collected either via REDCAP or Mirah. Procedures for this pre-pilot will be identical to for Aim 2 (see below) to identify challenges related to recruitment, randomization, and/or data collection. The only change to the Aim 2 procedures is that these pre-pilot cases will only be followed for 6 weeks, complete two rounds of research measures rather than three, and be paid up to \$20 for participation (a \$10 gift card for each round of assessment measures completed). The use of MBC is also part of consenting to the study, so the MBC measures from the pre-pilot have been uploaded as a study document (MBC Measures Pre-pilot). 15- to 30-minute cognitive interviews will be held with the five clinicians to refine measures and feedback reports, conducted by telephone or video conference immediately following clinical coaching calls. In cognitive interviewing, the participant's thinking 'out loud' when reviewing materials is recorded to assess how the clinician is viewing and interpreting them. Clinicians will review study mechanism measures to determine how they interpret the items and response options, ensure wording is clear, and ensure adequacy and accuracy of the items; they also to review a feedback report aloud. Each clinician will take part in up to 5 cognitive interviews during the pre-pilot. The interviews will be recorded and transcribed for coding. Following the pre-pilot and these interviews, final revisions will be made to study procedures and feedback reports as needed.

METHODS FOR AIM 2. PILOT EFFECTIVENESS IMPLEMENTATION HYBRID TRIAL

Design. This study will utilize a Type 1 Effectiveness Implementation Hybrid design, in which an effectiveness trial (Aim 2) is conducted while simultaneously gathering data to inform future implementation (Aim 3). The effectiveness trial will be a two-group RCT, with clients randomized to unidimensional or multidimensional MBC. The HCA clinics have agreed to randomize all of their youth clients to one of these two conditions, as they view this as a quality improvement initiative. Consent will be obtained from a subset of 400 clients and caregivers (i.e. the Research Subsample) to complete additional research measures. The implementation study will be a mixed-methods analysis.

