Procedures for effectiveness trial. After Aim 1 is complete, program-wide implementation of MBC will begin. The initial training will consist of a series of workshop style trainings conducted during regular agency staff meetings and ongoing consultation will be provided to agency staff thereafter. The training approach is a data-driven one, where questionnaires are used throughout the training and consultation to tailor implementation to that specific context. These questionnaires will be considered part of the implementation activities and will be administered to all staff members participating in the trainings. Clinicians who consent to be in the research study will be giving permission for these implementation data to be linked to the research data they provide for their clients; responses from other HCA staff will be de-identified and used to characterize the implementation under Aim 3. Prior to extracting these data for research purposes, we will submit a variable list to the IRB for approval. When the initial training is complete, the trial will begin program-wide at the participating HCA clinics. As the clinics add clients ages 11-17 to the Mirah system, the system will automatically randomize them to either unidimensional or multidimensional MBC on a 1:1 ratio. All clients and their caregivers will complete MBC measures as part of routine services, and the researchers will receive limited identifier datasets containing MBC data and Mirah metadata for all participants, an identifiable

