Quantitative Analyses. Aims 1b and 2 will involve using multilevel modeling (MLM) approaches¹²⁵, to account for nesting of repeated measures within clients and clinicians. In all Aim 2 models, we will treat site as a fixed effect, due to the limited number of clinics (n=3). For **Aim 1b**, on-track (OT) and not-on-track (NOT) algorithms will developed using an extant dataset^{46,47} (N = 597). Analyses will progress in two stages, following established procedures previously applied to the Outcomes Questionnaire system¹¹⁸⁻¹²⁰, the most widely-tested MBC system¹⁹. The first stage of the analysis involves generating expected change trajectories for SFSS scores over time. MLM will be used to estimate these individual change trajectories with weekly scores nested within participants, who are in turn nested within therapists. Models will be tested using the Hierarchical Linear Modeling (HLM) software package¹²⁶ and restricted maximum likelihood (RML) estimation. Prior to hypothesis testing, we will examine SFSS distributions and apply transformations (e.g., square root, logarithmic) for the weeks in treatment variable as necessary¹¹⁸.

The second stage of the analysis involves: (1) developing a system to identify cases at risk of showing treatment deterioration (NOT), and (2) testing its predictive accuracy. Identification of NOT cases is based on the expected change trajectories (intercepts, slopes, and random effects) estimated in Stage 1. Following Cannon et al¹¹⁸, we will split the data into two random samples, a reference sample and a validation sample. As a first step, the base rate of treatment

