Aim 2b will investigate potential factors associated with condition, client, or clinician that could influence a future SMART. GLMM (MLM with a logistic linking function) will be used to investigate factors associated with treatment and attrition from the study. In addition, differences between the full RCT sample (N = 900) and the Research Subsample (N = 400) will be examined utilizing data from electronic health records (EHR) to determine whether enrollment in the Research Subsample, and completing all 12 weeks, is associated with any demographic or clinical factors. We will also examine enrollment and attrition rates for clients within clinicians to determine whether any clinician factors might be associated with client-level participation in the study, along with comparing enrollment rates across clinics. As above, these analyses will inform design of the R01 SMART, including power analyses that take into account rates of NOT/OT and projected attrition.

MLM will also be used to compare the effects of study condition on SFSS change trajectories, Ohio Scores, and MBC mechanisms (**Aim 2c**). We will examine differences in MBC outcomes by feedback condition, nesting within treating clinician and controlling for clinic. If sample sizes in the research subsample prove too small for this analytic approach, analyses of variance will be used to test a time by treatment interaction. As a first step in comparing conditions on MBC mechanisms, we will aggregate the scores across sessions (within therapist) by averaging them or summing count variables (e.g., matches between a client being identified as NOT and the therapist recognizing deterioration) to create composite variables for each mechanism domain in Figure 2.

Finally, we will extend the MLMs tested to accommodate potential mediators and moderation by NOT status, diagnosis, and treatment type (**Aim 2d**). Mediation will be tested using the products of coefficients method¹²⁹, using bootstrapping to adjust for nonnormal, asymmetric confidence intervals¹³⁰. Algorithms for testing mediation using these methods are available in the package RMediation¹³¹ available in the software platform R. Moderation by NOT status will be tested by entering NOT status, along with the feedback condition by NOT

status interaction and other model covariates. Similar models will examine moderation by diagnosis and treatment type.

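### The mechanism composites name the therapist as the unit of aggregation although condition is assigned per client; followed literally, that rule removes the mechanism contrast, so the plan should state client-level composites

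*Combined protocol and SAP*

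**What the plan says.** Section 10 (Procedures Involved) makes the client the unit of randomisation. The Design paragraph describes a two-group trial "with clients randomized to unidimensional or multidimensional MBC", and the effectiveness-trial procedures say that, as clients aged 11-17 are entered, "the system will automatically randomize them to either unidimensional or multidimensional MBC on a 1:1 ratio". No section assigns clinicians to an arm, so one clinician can treat clients in both.

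Section 12 (Quantitative Analyses) introduces the multilevel models as a way "to account for nesting of repeated measures within clients and clinicians". For Aim 2c it gives the comparison: "We will examine differences in MBC outcomes by feedback condition, nesting within treating clinician and controlling for clinic". For mechanisms there is a preliminary step: "we will aggregate the scores across sessions (within therapist) by averaging them or summing count variables", which yields one composite per mechanism domain. Its example of a count is "matches between a client being identified as NOT and the therapist recognizing deterioration". Neither client nor condition is named as a level of aggregation. If the subsample proves too small, "analyses of variance will be used to test a time by treatment interaction". For Aim 2d these models are extended to mediators: "Mediation will be tested using the products of coefficients method".

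**The concern.** A condition contrast needs a mechanism value that can differ between clients in different arms. The one sentence that defines the mechanism variables groups scores by therapist, a level at which condition does not vary by design. An analyst who follows it would average or sum over a therapist's multidimensional and unidimensional clients together, and so lose the difference that Aim 2c is meant to measure.

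The stakes are considerable for a study whose Objectives call it mechanism-driven. A mechanism null produced by the way the variable was built would say nothing about measurement-based care, but it could still shape the larger trial this pilot is meant to inform. Leaving the unit open also allows it to be chosen after the data are seen.

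**Working it through.** **Inputs.** From Sample size and power calculations (section 12): 22 clinicians with 900 youth; at least 22 clinicians with 400 youth in the Research Subsample; 8% of outcome variance at clinician level. From section 7: up to 200 clinicians. From section 10: 1:1 allocation per client. Assumed: the 8% share also holds for mechanisms, caseloads are equal, and the true mechanism effect is d = 0.30 SD (0.25 and 0.50 were also run). The per-session mechanism item is collected only in the Research Subsample, so N = 400 is the relevant size for it; N = 900 is shown for range.

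**Plan's own figure.** There is none to reproduce. The stated power figures concern outcomes, and no effect size or power is given for mechanisms or the a-path.

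**Set-up.** For client i of clinician j, let M_ij = μ + u_j + d·T_ij + e_ij, with T_ij = 1 for multidimensional and 0 otherwise. One composite per therapist is then C_j = μ + u_j + d·p_j + ē_j, where p_j is the share of that clinician's clients in the multidimensional arm. C_j is the same number for every client of clinician j.

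**1. Literal reading, planned clinician-nested model.** The within-clinician coefficient is Σ(T_ij − p_j)(C_j − C̄_j) / Σ(T_ij − p_j)², where C̄_j is the mean of the composite over clinician j's clients. Because C_j is constant within clinician, C̄_j = C_j, every numerator term is 0, and so is the coefficient. With no residual variance within clinician, a random-intercept model gives the same answer. Fitted to simulated data for 400 youth with 22 and with 200 clinicians (trivial noise added so that the models converge), the largest absolute coefficient was 0.0004. If C_j is the mediator, a = 0 and a × b = 0.

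**2. Literal reading, one row per therapist.** A 22-row file contains no condition variable, only p_j.

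**3. Literal reading, clinician ignored.** The expected coefficient is d times the share of the variation in T that lies between clinicians. Under random allocation this is d × (J − 1)/(N − 1), and it does not depend on the 8%.

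| Youth N | Clinicians J | Clients per clinician | (J−1)/(N−1) | Expected at d = 0.30 | Simulated |
|---|---|---|---|---|---|
| 900 | 22 | 40.9 | 21/899 = 2.3% | 0.007 | 0.007 |
| 400 | 22 | 18.2 | 21/399 = 5.3% | 0.016 | 0.016 |
| 900 | 200 | 4.5 | 199/899 = 22% | 0.066 | 0.069 |
| 400 | 200 | 2.0 | 199/399 = 50% | 0.150 | 0.154 |

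This case is a bound, not a specified analysis. The plan nests within clinician, and its variance-analysis fallback tests a time interaction, whereas a composite over sessions has no time dimension.

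**4. Other readings.** A client-level composite, or one per therapist and arm, gave mean estimates of 0.297 to 0.304 across the same four settings for a true 0.30. With 400 youth and 22 clinicians the client-level composite gave 0.298 with power about .85 at d = 0.30, and 0.247 with power about .72 at d = 0.25.

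**The case against.** The strongest reply is that pooling is one reading of a parenthesis. The sentence aggregates over sessions and never says over clients or over arms. The parenthesis can mean session scores averaged for each client, with clients nested in therapist, or averaged per therapist and arm; step 4 shows that neither loses the effect. The context favours a client-level composite. The step is there to prepare a comparison by condition, the model is nested within clinician, clients are named as a level, mechanism items are collected from each youth and caregiver (section 10), and the count example is a client-specific event. That stands. It makes the finding conditional but does not remove it: the benign reading has to be inferred from other sentences against the only unit the rule names. Figure 2, cited for the mechanism domains, is not available to settle it.

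A reader might infer that the plan definitely pools the arms and would report no mechanism difference and no mediation whatever the truth. The documents do not support that. Besides the other readings, a therapist file has no condition variable and the nested model would be degenerate, so an analyst would probably notice. Nor is the effect nearly erased in every analysis. The 2% to 5% figures need about 22 clinicians and an analysis that ignores clinician; the subsample text says at least 22, and up to 200 are allowed. Finally, the text does not say that these composites are the Aim 2d mediators, so that link is an inference.

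**Conclusion.** The concern holds as a conditional one. The aggregation rule names a unit that conflicts with the unit of randomisation. If one value per therapist is formed, the condition coefficient in the planned nested model is 0 for any number of clinicians. The zero a-path and product rest on the further assumption that these composites are the mediators. If clinician is ignored, between 2% and 50% of the effect remains over the range of sample sizes and clinician numbers in the documents. If composites are formed per client, or per therapist and arm, nothing is lost.

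The zero and the (J−1)/(N−1) shares follow from the algebra; the simulated estimates and power also rest on the 8% clinician share, equal caseloads and the chosen effect sizes. Severity is moderate: the primary endpoints in section 9, the SFSS and Ohio scales, do not use these composites, but the mechanism comparison in Aim 2c does, and Aim 2d may.

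**What to change.** In the Aim 2c paragraph of section 12, replace the therapist with the client as the unit of aggregation, so that scores are combined across sessions within client. State that these client-level composites are the Aim 2c mechanism outcomes and the Aim 2d mediators, with clinician kept as the nesting level. Express count variables per session. Summed counts would otherwise scale with the number of sessions and, if taken per therapist, with caseload as well.

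This is a wording change that uses the data already planned. Its cost is that client composites are noisier than therapist means.

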dataset for individuals who consent to take part in the research subsample. We have uploaded a variable list of the variables we will be requesting from Mirah. After the first time a youth and their caregiver complete the MBC measures, the Mirah system will proceed to screens with recruitment and consent information for participation in the Research Subsample. Youth and caregivers will be asked to assent/consent to complete additional research measures. Each time they complete Mirah measures for routine sessions, youth and caregivers will be administered one additional mechanism item; this item will be included in up to 12 sessions after they enroll in the study. In addition, they will complete a longer set of research measures will including the Ohio Scales and additional mechanism measures; these will be administered at study enrollment, 6 weeks later, and 12 weeks after study enrollment. These longer sets of research measures will be administered via the REDCap system, with links e-mailed directly to the family by research staff. Additional Research Subsample Measures have been uploaded under Study Documents. Families who consent to be a part of this Research Subsample will be paid up to \$30 for completing these measures (the project will e-mail them a \$10 gift card per major assessment completed either directly through e-mail or by using Qualtrics and Tango Card). Clinicians treating clients in the Research Subsample will also be asked to complete additional measures for those clients and will be paid \$36 for completing those measures. The Mirah system does not have a way to only recruit clients whose clinicians have consented to be in the research study or to tailor the measure schedule for those clients. Therefore, if a client agrees to be in the study and their clinician has not, the study will contact the clinician, let them know that they will be receiving links to research measures, and see whether they would like to consent to be in the study at that point. If they do not, then they will be instructed to disregard the requests for them to complete measures. These measures are also included in the Research Subsample Measures upload under Study Documents.

METHODS FOR AIM 3. MIXED-METHODS ANALYSIS OF IMPLEMENTATION FACTORS

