deterioration—a significant worsening of symptoms over the course of treatment—will be identified in the reference sample. Consistent with previous studies¹¹⁸⁻¹²⁰, identification of the base rate will be based on a combination of the reliable change index¹²⁷ (RCI) and clinical cutoff scores. Established SFSS values for the RCI and the clinical cutoff score¹²⁸ will be used to identify cases with clinical deterioration, operationalized as an SFSS increase over treatment exceeding the RCI and a case ending treatment in the clinically significant range of functioning. The deterioration base rate from the reference sample will serve as a basis for deriving prediction intervals around the expected mean change trajectory in the validation sample. Cases identified as exceeding the prediction interval at any point during treatment will comprise the NOT group. Cases within the interval form the OT group.

The validation sample will then be used to check the validity of the warning system in predicting true treatment deterioration. Analyses will examine whether classifying a client as NOT accurately predicts whether they end treatment classified as deteriorated. Sensitivity and specificity will be calculated and the algorithms will be adjusted as needed until adequate levels are reached, using Cannon et al.’s¹¹⁸ specificity values of .55 and specificity values of .75 as guides. We will then test the predictive validity of the finalized OT/NOT algorithm (**Aim 2a**) using the full RCT sample (N = 900). To prepare for the SMART R01, we will also conduct simulations, varying estimates entering the expected change trajectories to investigate transition points in the OT/NOT intervals to assess optimal timing of when to conduct the second randomization.

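### Aim 2d sets no time order between mediator and outcome, so symptom-driven change in a mechanism can be reported as mediation

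*Combined protocol and SAP*

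**What the plan says.** All the analysis text is in Section 12 (Data Management), under Quantitative Analyses.

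- **Construction of mechanism variables (Aim 2c).** "As a first step in comparing conditions on MBC mechanisms", the plan says, "we will aggregate the scores across sessions (within therapist) by averaging them or summing count variables". No cut-off session or week is given. The example of a count is "matches between a client being identified as NOT and the therapist recognizing deterioration".
- **Mediation (Aim 2d).** "we will extend the MLMs tested to accommodate potential mediators and moderation by NOT status", and "Mediation will be tested using the products of coefficients method", with bootstrapped intervals and the RMediation package. No mediator variable is named. No mediator window, lag, prior-symptom adjustment or reverse-path check is stated.
- **NOT status.** It comes from the SFSS trajectory: "Cases identified as exceeding the prediction interval at any point during treatment will comprise the NOT group".
- **Data collection (Section 10, Procedures for effectiveness trial).** Research Subsample families answer one extra mechanism item at routine sessions: "this item will be included in up to 12 sessions after they enroll in the study". Of the longer set, which holds the Ohio Scales and further mechanism measures, the plan says that "these will be administered at study enrollment, 6 weeks later, and 12 weeks after study enrollment". The Section 8 timeline has the MBC measures given at every session.

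**The concern.** Randomisation protects the path from condition to mechanism. It does not protect the path from mechanism to outcome, which is observational. A composite taken over the whole course of sessions includes mechanism scores recorded after much of the symptom change has happened. A youth who is getting better may become more engaged or rate the alliance higher, and the composite then predicts the SFSS trajectory even if engagement does nothing. The count example goes further. It can accrue only once the SFSS has gone outside its expected band, so for SFSS outcomes the mediator is built partly from the outcome.

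Section 3 calls the study mechanism-driven, and Section 4 describes MBC mechanisms as still largely theoretical. A mediation analysis that cannot tell mechanism acting on symptoms from symptoms acting on mechanism would not advance that question. The randomised comparisons of SFSS and Ohio scores in Aim 2c are not affected.

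**Working it through.** The plan gives no power, effect size or error rate for mediation, so there is no figure of its own to reproduce.

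**1. Why the bias arises.** Let X be condition, S(t) symptoms and M(t) the mechanism at session t. Suppose X affects S, S affects M with strength k, and M has no effect on S. Then true mediation is zero.

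- Path a (X to the mean of M) = k × (effect of X on S, averaged over the sessions used). It is non-zero if X affects S and k is not 0.
- Path b (mean of M to outcome, given X) is causally zero. Its estimate is not, when k is not 0, because the mean of M carries symptom information from the sessions that make up the outcome.
- The product a × b is therefore non-zero when both links exist.

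Two limiting cases check this. If X does not affect S, a = 0 while b is nearly always significant, so the false-positive rate should be about 5%. If k = 0, both paths are null and the rate should be about .05 × .05 = .0025.

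**2. Inputs.** From Section 12, Sample size and power calculations: 400 adolescents, 22 clinicians, 8% clinician variance, d = .30 and .25, p = .05 (two-sided assumed). From Section 10: 1:1 allocation and up to 12 sessions (12 assumed). Assumed, because the documents give nothing: the symptom-to-mechanism strength and the persistence of symptoms. Test: product of coefficients with a 95% Monte Carlo product interval in place of the bootstrap.

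**3. False indirect effects with the all-session mean.** n = 400, 400 replicates per cell, adjusted for clinician; the week-12 model also adjusts for baseline symptoms and baseline mechanism.

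| d | Outcome | k = 0 | k = .3 | k = .5 | k = .7 |
|---|---|---|---|---|---|
| .30 | week 12 | 1% | 11% | 26% | 33% |
| .30 | SFSS slope | 0.2% | 6% | 16% | 25% |
| .25 | week 12 | 0% | 10% | 22% | 27% |

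Monte Carlo error is at most about 2.5 points (√(.5 × .5 / 400) = .025). With d = 0 the rate was 4-7%, and with k = 0 at most 1%, matching the two limiting cases. The apparent share mediated was about 7%, 18-20% and 31-33% for k = .3, .5 and .7.

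**4. Other assumed dynamics, n = 400.**

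- d = .30, reverse coefficients .2/.3/.4 (1,000 replicates): 6%/14%/18%. Path b alone was falsely significant in 82%/99%/100%.
- d about .27, reverse coefficients .1-.4: 4-49%.
- d about .30, reverse coefficients .2-.4, different autoregression: 22-69%.

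Strength is not on one scale across these sets, so they show direction and spread, not an estimate.

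**5. Effect of time ordering.** Mediator from sessions 1-5, outcome at week 12, n = 400, d = .30:

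| Adjustment | k = .3 | k = .5 | k = .7 |
|---|---|---|---|
| Baseline only | 3% | 7% | 10% |
| Plus week-6 symptoms | 0% | 2% | 6% |
| Plus symptom history, weeks 0-6 | 0.2% | 0% | 0.5% |

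Under the d about .27 dynamics, full history gave 1% or less, and baseline plus week-6 symptoms up to 4%. An early window alone is not enough.

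**6. Cost in power.** With true mediation and no reverse path, detection fell from 40-100% (all-session mean) to about 8-63% (early mediator with adjustment). In another set with true mediation (total d about .10-.34) it was 9-24% against 86-100%, the latter partly inflated by the same bias where a reverse path was present. The low error rates in step 5 therefore partly reflect a weak test. The session-level lagged model was not simulated.

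**The case against.** The strongest reply is that the plan never says that the all-session composite is the Aim 2d mediator. The aggregation sentence belongs to Aim 2c and is called a first step, count variables are summed and not averaged, and week-6 mechanism scales exist, so a time-ordered mediator is compatible with the text. The mechanism domains are in a figure not available here, and the phrase about aggregating within therapist leaves open whether the composite is at client or clinician level. All of this stands: use of the composite in Aim 2d is an inference. But Aim 2d extends the Aim 2c models and defines no other mediator. If the composite is not meant, the mediator and its timing are undefined, and the same text is needed.

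Three stronger readings are not supported.

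- A reader might infer that false mediation *would* be reported. In most of the settings shown, most simulated trials reported none, and the rate is nominal or lower if condition does not move symptoms or symptoms do not move the mechanism. The 82-100% figure is path b alone, which the product test does not report as mediation.
- A reader might apply the point to the full sample of 900. The session mechanism item and the mechanism scales go only to the Research Subsample, so n = 400 is the relevant size.
- A reader might infer that the mediation result is a stated input to the next grant. The documents tie that grant to procedures, mechanism measures, implementation strategies, on-track simulations and the enrolment and attrition analysis.

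Pilot status and power calculations confined to Hypothesis 2c.1 excuse low power for mediation. They do not excuse an analysis whose direction cannot be read.

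**Conclusion.** The point holds as a gap with a predictable bias. Aim 2d fixes no order between mediator and outcome, and the only mechanism variables constructed overlap the SFSS trajectory. At n = 400 with no true mediation, the false indirect-effect rate was roughly 4-50% in three sets of assumed dynamics and reached 69% in a fourth. These figures require that condition moves symptoms, with d about .25-.30 (the Research Subsample effects used in the plan's power section), and that symptoms move the mechanism at a strength the documents do not give. No single rate should be quoted as the size. The dependence of the count example on NOT status follows from the plan's own definitions and needs no simulation. The text should be amended before the mediation analysis is run.

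**What to change.** Amend the Aim 2d text so that any mediation claim rests on one of two time-ordered analyses, chosen in advance:

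- a session-level lagged (cross-lagged) multilevel model, in which mechanism at one session predicts symptoms at a later one and the reverse path is estimated too; or
- mechanism scores up to week 6, counted in calendar time from enrolment, predicting week-12 Ohio scores or later SFSS, adjusted for baseline mechanism and the SFSS history up to the mediator, not only baseline and week-6 SFSS.

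In addition, keep counts derived from NOT status or the SFSS out of SFSS mediation models, report the all-session composite as a descriptive association only, and state whether composites are formed per client or per clinician.

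The cost is a few sentences and no new data. The downside should be written into the plan: the week-6 version uses fewer sessions, can lose substantial power and misses effects already expressed by week 6, so a null result there must not be read as no mediation. The session-level model uses all sessions, but its error rate and power should be checked by simulation before it is adopted.
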